- Title: The Effects of the Histamine-3 Receptor Inverse Agonist Pitolisant on Alcohol Self-Administration in Heavy Drinkers The present study will involve 72 men and women aged 21 to **Population:** 55 who exceed safe levels of drinking. Women and minorities who meet the study criteria will be eligible to participate. No vulnerable populations are being targeted for inclusion in this study. Intervention: Eligible subjects will receive a dose of 8.9 mg (two 4.45 mg pills) of pitolisant or a matched placebo once daily over a 7day period and a dose of 17.8 mg (one 17.8 mg pill) of pitolisant or matched placebo once daily over a 5-day period. A 25 mg riboflavin tracer will be added to each 4.45 mg capsule and 50 mg riboflavin tracer will be added to each 17.8 mg capsule to serve as an objective measure of medication adherence. Subjects will take study medication by mouth. Subjects will receive alcohol in the laboratory on day 12 in an alcohol craving challenge. Subjects will be presented with four drinks, each mixed to raise their BAL 0.0125g/dl. They will be told that they can either consume the desired number of drinks over the following 60 minutes or they will receive the equivalent in a cash reward. This procedure will be repeated with an additional 4 drinks after 60 minutes has elapsed. Subjects will serve as their own controls. The intervention will be repeated with a placebo/pitolisant after a washout period. The order of pitolisant and placebo dosing will be randomized. The specific objective of this study is to determine whether **Objectives:** pitolisant, an H-3 receptor inverse agonist that is FDAapproved for treating narcolepsy, has effects on alcohol craving and consumption. Testing the effects of pitolisant on drinking is a compelling opportunity that is consistent with the mission of NIAAA to evaluate the efficacy of re-purposed compounds with novel mechanisms that have the potential to treat AUD. If successful, this study could lead to a phase II randomized controlled trial to test pitolisant as a treatment for AUD. The specific goal of this study is to evaluate the effects of pitolisant on drinking and craving among heavy drinkers in a human laboratory using an alcohol self-administration paradigm.
- 2 Protocol Summary

Design/Methodology:	This is a double-blind, randomized, placebo-controlled, crossover design trial that will test the effect of pitolisant on alcohol self-administration and craving following a priming dose of alcohol. An established human laboratory self- administration procedure will be followed. Each subject will complete 5 clinic visits over a period of up to 66 days of participation. Study participation is comprised of a baseline assessment, randomization visit, alcohol self administration Trial 1, an assessment visit to verify continued eligibility and dispense medication, and a second alcohol self-administration Trial. The volume of alcohol consumed during alcohol challenge trials 1 and 2 will be used to test the effect of pitolisant on alcohol consumption. Craving measures (AUQ and VAS) collected during the self-administration trials will be used to test the effect of pitolisant on alcohol craving.
Total Study	The entire study will take 24 months to complete.
Duration:	
Subject Participation	Each subject's length of participation will be up to 66 days.
Duration:	

### 3 Background/Rationale & Purpose

#### 3.1 Background Information

Current models of care for treating Alcohol Use Disorder (AUD) include both behavioral therapies and pharmacotherapy. Although pharmacotherapy for AUD in the US has been available since 1948 when disulfiram was approved, options for treatment are limited as there are only four medications which have been approved by the FDA for treating AUD. Disulfiram, naltrexone, acamprosate, and long-acting naltrexone have all shown promise as agents to treat AUD but no single medication has proven to be effective across the heterogeneous groups of people with AUD. Movement towards models of personalized care and pharmacogenetic treatment matching hold some promise for improving AUD treatment outcomes, but the limited number of unique mechanisms of action of the currently approved drugs presents a challenge to implementing this model of care. Unfortunately, few novel compounds to treat AUD progress to phase II trials, and developing novel compounds is both costly and timeconsuming. One pathway of drug development efforts has been focused on re-purposing FDA approved medications that have promising mechanistic effects and some success data has supported the use of H3 receptor antagonists as haing potential to modulate craving and consumption. Identification of additional drugs with unique mechanisms of action that are found to reduce alcohol consumption could expand the treatment options and further the goal of personalized care for AUD. The overarching goal of our research is to identify agents with unique mechanisms that hold promise for treating AUD. The specific objective of this study is to determine whether pitolisant, an H-3 receptor inverse agonist that is FDA-approved for treating narcolepsy, has effects on alcohol craving and consumption. Alcohol Use Disorder as a national health problem

More than 16 million adults suffer from Alcohol Use Disorder (AUD) in the United States9. The economic burden of this is estimated to be 249 billion dollars and approximately 88,000 Americans die from alcohol-related causes each year. Untreated AUD is associated with an increased risk of accidents, injuries, suicide, and worsening of other health comorbidities and it is the third most preventable cause of death in the US. Treating addiction more effectively has become a priority of national importance and the Surgeon General has urged researchers to undertake testing of new treatments to combat addiction. The present study is intended to answer the call for accelerating drug development for AUD by exploring the potential to repurpose an existing drug as a treatment for AUD.

#### Rationale for developing pitolisant as an agent to treat AUD

H-3 histamine receptors are one of the four types of presently known histamine receptors. These G protein-coupled receptors are present predominately in the brain and are implicated in the regulation of a variety of behaviors including those related to cognitive function, locomotor activity and anxiety. The finding that the density of binding of an H-3 receptor ligand was lower in insular cortical, accumbal, and hippocampal brain regions in alcohol-preferring rats (AA) as compared to alcohol-avoiding rats provided some of the first evidence that brain H-3 receptors may play an important role in the regulation of alcohol consumption. Further evidence of this includes the observation that H-3 receptor knock-out mice derived from the C57B/6J strain consume less alcohol than wild type mice of this strain. Numerous studies have shown that the administration of either H-3 receptor antagonists or H-3 inverse agonists/antagonists (i.e. ciproxifan clobenpropritor or thioperamide) reduces ethanol consumption in rats and mice . In contrast, the administration of H-3 receptor agonists increases the self-administration of alcohol by AA rats. Conditioned place preference studies indicate that H-3 receptor antagonists and inverse agonists/antagonists reduce alcohol-related reward. This may be a factor that explains the reduction of alcohol consumption produced by these agents. It should be noted, however, that the administration of ciproxifan or the H-3 receptor antagonist conessine, failed to block ethanol-induced place preference in certain strains of mice, namely C57BL/6Sca and Swiss mice, respectively. Cue-induced reinstatement of responding by mice for alcohol is attenuated by the administration either of the H-3 receptor antagonist JNJ-39220675 or by ciproxifan, suggesting that these agents may decrease alcohol cue-induced craving.

While much of the research based on animal studies indicates that pharmacological blockade of H-3 receptors may lead to reductions in the drinking of alcohol, the degree to which these studies will translate to human alcohol consumption in individuals with AUD remains to be determined. Ligand binding studies do indicate that H-3 receptors are located in several areas of the human brain that are linked to the regulation of alcohol consumption including the nucleus accumbens, insular cortex, and anterior cingulate.

Recently the FDA has approved the H-3 receptor inverse agonist/antagonist pitolisant for the treatment of excessive daytime sleepiness and catalepsy in narcolepsy patients. The Ki of this drug as an antagonist of the recombinant human H-3 receptor is 0.16 nm, and its E50 for its action as an inverse agonist at these receptors is 1.5 nm^13. In contrast, the Ki for pitolisant at H1, H2, and H4 receptors are in the micromolar range indicating that this drug has a high degree of selectivity for the H-3 receptor. The therapeutic effects of pitolisant in narcolepsy patients may be mediated by the activation of histaminergic neurons resulting from the blockade of presynaptic H-3 receptors. The presynaptic actions of this drug promote the release of

histamine. Increased histamine release in the nucleus accumbens produced by the administration of ciproxifan was found to correlate with reductions in alcohol seeking behaviors. Whether the histamine releasing actions of drugs that counteract H-3 receptor activation can account for their suppressant effects on alcohol consumption in rodents is still being studied. Some authors have postulated that these effects may be related by the blockade of the effects of dopamine resulting from inhibition of H-3/dopamine heteroreceptors in the nucleus accumbens. Pitolisant, in contrast to stimulants such as amphetamine that are abused, has not been found to elevate levels of mesolimbic dopamine.

In healthy volunteers who were moderate drinkers, enhanced bold signals in the striatal areas including the nucleus accumbens were found to correlate with stimulation ratings during alcohol infusion. This finding suggests that alcohol-induced stimulation involves activation of the brain linked to the reinforcing effects of many drugs of abuse. One group of investigators has found that heavy drinkers may be more sensitive to the stimulant effects of alcohol than are light drinkers as measured on the ascending limb of the blood alcohol curve and suggest that continued sensitivity to the stimulant effects of alcohol may be one of the factors that contributes to the continued alcohol consumption in AUD. Given the possible role of alcohol stimulant effects in facilitating drinking and that pitolisant has what can be construed as stimulant-like properties such as decreasing daytime sleepiness and in enhancing alertness, it is important to determine that this drug will not enhance the stimulating effects of alcohol in drinkers. We hypothesize that it will not for several reasons. Pitolisant as compared to psychomotor stimulants such as amphetamine does not increase the release of dopamine in the nucleus accumbens, which may play a key role in mediating the reinforcing effects of many drugs of abuse. Unlike psychomotor stimulants pitolisant is not self-administered by primates, an established animal model of abuse liability. More importantly, among people who use stimulants, drug liking and willingness to use the drug did not differ significantly between pitolisant and placebo. In this study we will examine whether pitolisant increases the stimulant effects of a priming drink of alcohol as assessed using the biphasic alcohol effects scale (BAES).

In narcolepsy patients, pitolisant is well tolerated but may produce some adverse effects such as insomnia and sleep disturbance that may be related to its activation of the systems that mediate this drug's therapeutic effects. In healthy human subjects, single oral doses of pitolisant at doses several times above those currently recommended for therapeutic use were well tolerated with EEG evidence of increased vigilance and enhanced attention being detected at the end test days. The H-3 receptor antagonist, ABT-288, also has been reported to be well tolerated when it was administered to healthy young adults. Thus, it is anticipated that pitolisant should be well tolerated in subjects who do not have narcolepsy.

#### 3.2 Rationale and Purpose

This proposal holds significant innovation as there is strong evidence that medications that act as inverse agonists at the H-3 receptor decrease alcohol consumption and its rewarding effects. There are currently no published clinical studies concerning the effects of either H-3 receptor inverse agonists/antagonists or of H-3 receptor antagonists on alcohol consumption. This proposed study answers the call for accelerating the development of medications for AUD by testing a commercially-available and well-tolerated agent at a fraction of the cost of developing novel therapies. This proposal is innovative as no other human studies have explored

the H-3 receptor systems as a target for medications to treat alcohol use disorder. Given the compelling preclinical findings that H-3 inverse agonists/antagonists modulate craving and consumption, testing this mechanism in a human laboratory is the next logical step in drug development.

## 4 Objectives

4.1 Study Objectives

The specific objective of this study is to determine whether pitolisant has effects on alcohol craving and consumption. Testing the effects of pitolisant on drinking is a compelling opportunity that is consistent with the mission of NIAAA to evaluate the efficacy of re-purposed compounds with novel mechanisms that have the potential to treat AUD.

#### 4.2 Study Outcome Measures

4.2.1 Primary Outcome Measures

The primary outcomes are alcohol consumption and cravings during the alcohol selfadministration trials. Drinking volume during the alcohol self-administration will be measured to evaluate the effects of pitolisant vs. placebo on the rate of alcohol consumption after a priming drink. Alcohol craving will be measured using the Visual Analog Scale (VAS) and the Alcohol Urge Questionnaire (AUQ) during the alcohol self-administration trial. These self-report measures of craving will be used to evaluate the effect of pitolisant on craving vs. placebo.

#### 4.2.2 Secondary Outcome Measures

Secondary outcome measures for this study include the effect of pitolisant on 1) stimulant effects of alcohol, and 2) alcohol consumption and craving and sleep quality during the medication exposure period. The Biphasic Alcohol Effects Scale (BAES) will be used to assess the effects of pitolisant administration on the stimulant effects of alcohol. The Obsessive-Compulsive Drinking Scale (OCDS) and alcohol Visual Analog Scale (VAS) will be used to assess the effects of pitolisant on craving during the medication exposure period. Sleep Diaries will be used to assess the effects of assess the effects of pitolisant on sleep quality during the medication exposure period.

#### 5 Study Design

This is a double-blind, randomized, placebo-controlled, crossover design trial that will test the effect of pitolisant on alcohol self-administration and craving following a priming dose of alcohol. An established human laboratory self-administration methodology developed by O'Malley and her colleagues will be followed. The O'Malley self-administration methodology entails subjects consuming a priming drink of alcohol and subsequently participating in two one-hour self-administration sessions. In each session subjects receive four alcoholic drinks which

they may either drink, or otherwise receive compensation for not consuming. Confirmation of the validity of this approach as a method for screening for medications to treat AUD include the finding that pre-treatment with naltrexone significantly reduced alcohol consumption when the O'Malley methodology was used. Using this method, our group has found that the anticonvulsant zonisamide reduces alcohol consumption in non-treatment seeking social drinkers. We later confirmed that the administration of zonisamide decreases alcohol consumption in subjects with AUD in a double-blind randomized clinical trial as have other investigators. Testing pitolisant using this self-administration methodology is the next logical step in drug development given the strong evidence that the H-3 receptor inverse agonist/antagonists reduce drinking in animal models. The human laboratory-based alcohol self-administration methodology is cost effective and time-efficient for testing novel drug candidates for AUD treatment.

*Subjects:* Heavy-drinking subjects will be enrolled to increase the potential generalizability of these findings to a clinical AUD population. Subjects will be recruited through advertising, study flyers, internet postings, and an established subject registry at Boston Medical Center. Interested subjects will be screened by telephone to determine initial eligibility prior to the baseline assessment.

## 6 Potential Risks and Benefits

#### 6.1 Risks

#### **Risks of study medication**

To minimize the risk of adverse health events we will instruct subjects to contact study staff with any questions or concerns about changes in health effects after initiating study medication/placebo. Trained medical staff will evaluate any reported adverse effects and make a clinical determination about management through dosing methods, dose discontinuation, and/or referral for medical care. If subject cannot tolerate the escalation in dose of study medication during the medication exposure period, their participation in the study will be discontinued and they will be instructed to stop taking the study medication immediately Subjects will be given a wallet card that includes a phone number with 24/7 coverage for medical emergencies. As an added safety precaution, subjects will be contacted three times mid-week of the medication exposure period for an adverse effect assessment.

#### Adverse events

The following adverse reactions were observed in data collected for 266 patients with narcolepsy, 114 of which received a placebo. The incidence of the following adverse reactions of pitolisant versus placebo were as follows: Headache (18% vs 15%), Insomnia (6% vs 2%), Nausea (6% vs 3 %), Upper respiratory tract infection (5 % vs 3 %), Musculoskeletal pain (5% vs 3%), Anxiety (5 vs 1%), Heart rate increased (3% vs 0%). In post marketing reports, the following adverse effects have been recorded: fatigue, weight gain, epilepsy, abnormal behavior and dreams, bipolar disorder, depression/depressed mood, sleep disorders, nightmares,

Pitolisant effects on alcohol self administration and craving in heavy drinkers Version 1.10 7.7.2022 suicidality, and pruritus. Post marketing reports of side effects are uncertain in causality and because the population size is unknown, the rates of these effects cannot be determined. Although pitolisant has wakefulness effects, it has not been found to have a strong potential for misuse.

Pitolisant can reduce the reliability of hormonal contraceptives, and it's dosing is altered by concomitant use of strong CYP2D6 inhibitors and CYP3A4 inducers. The pharmacodynamic effects of pitolisant may be blocked by the administration sedating histamine-1 receptor antagonists. Use of pitolisant can result in QT interval prolongation, especially when taken with other drugs that prolong the QT interval. Preclinical studies have found a risk of exposure during pregnancy with doses four times greater than the maximum dose. Given that the risk is unknown in humans, pregnant women should avoid exposure to pitolisant.

To protect against the risk of altered drug metabolism for subjects taking strong CYP2D6 inhibitors and CYP3A4 inducers, we will exclude subjects taking any of these medications. Subjects known to be poor CYP2D6 metabolizers (PMs) will also be excluded due to risk of higher pitolisant concentrations. Subjects who need to take sedating H-1 receptor antagonists will be excluded because these drugs may block the CNS effects of pitolisant.

Given that pitolisant is largely metabolized by the liver, subjects will be excluded from this study who have any clinically significant hepatic disease. Because the pharmacokinetics of pitolisant are unknown among people with renal disease, subjects will be excluded for renal insufficiency.

To protect against the risk of QT prolongation, subjects taking other medications which have this adverse effect will be excluded and we will exclude subjects whose have QTc interval > 450 msec. Subjects will also be excluded if they have a history of any clinically significant cardiac disease or a family history of long-QT syndrome.

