#### 7.2 Subject Exclusion Criteria

An individual who meets any of the following criteria will be excluded from participation in this study:

- 1. Does not have a smartphone to complete medication exposure period study assessments
- 2. Seeking treatment for alcohol problems
- 3. Clinical Institute Withdrawal Assessment at  $\geq 10$
- 4. DSM-5 diagnosis of current major depression, bipolar disorder, schizophrenia, bulimia/anorexia, insomnia disorder or a substance use disorder other than alcohol, nicotine, marijuana or caffeine
- 5. If female, pregnant, nursing, have plans to become pregnant
- 6. If female, does not agree to use an accepted form of birth control
- 7. Has a medical contraindication to the use of pitolisant
- 8. Has diagnosed medical or mental condition for which further alcohol exposure at the planned dose range would be contraindicated
- 9. Current risk of suicidality (MINI suicidality score greater than 8 (low risk) or Yes to the ideation question #4 of the C-SSRS)

- 10. BMI is greater than 40 or less than 18
- 11. Impaired renal function (GFR <80 mL/min)
- 12. Has a history of any clinically significant renal or hepatic disease
- 13. Child-Pugh Score equal to or greater than Class B (evaluated based on presence or absence of encephalopathy and ascites, INR, bilirubin, and albumin) [https://www.mdcalc.com/child-pugh-score-cirrhosis-mortality]
- 14. Has a clinically significant ECG as determined by the investigator or abnormal ECG heart rate (<45 or >100 bpm) or QTc interval corrected for heart rate using the Fridericia formula (QTcF) > 450 msec
- 15. Has a history of cardiac arrhythmias or who for other reasons are at risk for developing Torsade de Pointes including those with bradycardia, hypokalemia, and congenital QT interval prolongation
- 16. Has a history of dementia
- 17. Has received alcohol counseling or other non-pharmacologic intervention to treat AUD in the past 90 days
- 18. Has taken medications that are used to treat AUD in the past 90 days
- 19. Is currently taking medication that is a sensitive CYP3A4 substrate
- 20. Is currently taking a QTc prolongation agent
- 21. Has urine toxicology results positive for cocaine, opioids, amphetamines, buprenorphine, methadone, methamphetamines, oxycontin, barbiturates, or benzodiazepines.

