- 22. Subject is taking a medication which will significantly alter drug metabolism (e.g., strong CYP2D6 inhibitors, strong CYP3A4 inducers, or H1 receptor antagonists that cross the blood barrier (e.g. diphenhydramine or meclizine).
- 23. Subject has known hypersensitivity to pitolisant and any of its components, riboflavin, and/or lactose.
- 24. Subject is known to be a poor CYP2D6 metabolizer.
- 25. Subject is unable to comfortably abstain from nicotine for a period of 8 hours.
- 26. Has COPD, history of solid organ transplant, sickle cell disease, severe heart disease or other health condition for which exposure to COVID-19 represents an unreasonable risk as determined by the study staff physician using accepted COVID-19 guidance (e.g. Centers for Disease Control, etc.).

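### Section 7.2 does not list family history of long-QT syndrome and carries only part of the cardiac-disease exclusion that Section 6.1 promises

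*Combined protocol and SAP*

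**What the plan says.** Section 6.1 (Risks of study medication, Adverse events) states that pitolisant can prolong the QT interval and lists the protections. Subjects on other QT-prolonging drugs or with a QTc above 450 msec are kept out. It then adds, without qualification: "Subjects will also be excluded if they have a history of any clinically significant cardiac disease or a family history of long-QT syndrome".

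Section 7.2 is the formal list. It opens with "An individual who meets any of the following criteria will be excluded from participation in this study" and runs to 26 items. Those nearest to the 6.1 commitment are:

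- Item 12: "Has a history of any clinically significant renal or hepatic disease".
- Item 14: "Has a clinically significant ECG as determined by the investigator or abnormal ECG heart rate", with limits on heart rate (below 45 or above 100 bpm) and QTcF (above 450 msec).
- Item 15: "Has a history of cardiac arrhythmias or who for other reasons are at risk for developing Torsade de Pointes", with bradycardia, hypokalemia and "congenital QT interval prolongation" given as inclusions.
- Item 26: "Has COPD, history of solid organ transplant, sickle cell disease, severe heart disease", in a criterion about COVID-19 exposure that refers to the study physician's judgement.
- Items 7 and 8: general criteria for a contraindication to pitolisant and for a condition that rules out the planned alcohol exposure. Neither is defined further.

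Section 6.3 calls the risk/benefit ratio favorable, relying on the protections in place. Appendix A marks the ECG at the baseline visit only.

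**The concern.** Two sections of one protocol give different answers about the same person. Section 6.1 is categorical on both cardiac history and family history. Section 7.2, the list presented as the exclusion criteria, is silent on one and narrower on the other.

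This looks like an omission rather than a choice, because the other medication-risk exclusions in that part of 6.1 do reach 7.2: QT-prolonging drugs (item 20), the 450 msec limit (item 14), strong CYP2D6 inhibitors, strong CYP3A4 inducers and sedating H1 antagonists (item 22), known poor CYP2D6 metabolizers (item 24), hepatic disease (items 12 and 13) and renal insufficiency (item 11).

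At stake is whether the protections that the IRB weighs under 6.3 are those applied at screening. Staff who work from 7.2 and staff who work from 6.1 could reach different decisions on the same subject.

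**Working it through.** No arithmetic enters the eligibility comparison. The check sets each 6.1 commitment against all 26 items of 7.2 and then follows two example subjects through the list.

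**Commitment by commitment**

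| Section 6.1 | Nearest items in 7.2 | Covered? |
|---|---|---|
| Family history of long-QT syndrome | Item 15 names the subject's own congenital prolongation; no item mentions relatives | Not expressly |
| Any clinically significant cardiac disease, by history | Item 12 has the parallel wording but names renal and hepatic disease only; item 14 acts on the ECG finding; item 15 on arrhythmia or Torsade risk; item 26 on severe heart disease | In part |

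The qualifier in item 26 about COVID-19 risk can be read as applying to the whole list or only to its last element. On either reading the threshold for heart disease is severe, which is narrower than clinically significant.

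**Example A.** A relative has long-QT syndrome. The subject's QTcF is 440 msec, and there is no personal congenital prolongation or arrhythmia.
- Section 6.1: excluded.
- Item 14: not met, since 440 is not above 450.
- Item 15: no named condition is met. Exclusion needs the investigator to treat family history as one of the other reasons for Torsade risk.
- Item 7: met only if family history is judged a contraindication.
- Express 7.2 criteria: passed.

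**Example B.** The subject has clinically significant cardiac disease that is neither severe nor arrhythmic, with an acceptable ECG.
- Section 6.1: excluded.
- Item 12: not met, because cardiac disease is not named.
- Item 14: not met, because the ECG is acceptable.
- Item 15: no arrhythmia and no named condition; otherwise a matter of judgement.
- Item 26: not met, because the disease is not severe.
- Items 7 and 8: possible, at discretion.
- Express 7.2 criteria: passed.

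**What happens after entry.** Each period has 7 days at the lower dose and 5 at the higher, 7 + 5 = 12 days. Two periods make 2 × 12 = 24 days of capsules. The design is a placebo crossover, so 12 of those days are on pitolisant. Appendix A gives one scheduled ECG occasion, at baseline, and none during either period. The reasons for discontinuation at medication visit #2 (Section 9) include no cardiac finding. Vital signs, concomitant medications and adverse events are checked at every visit, and each period has three adverse-event calls (Section 10.2 and Appendix A).

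**Can the history be collected?** Section 9 lists a general medical screen, physical examination and ECG at baseline, and Appendix A lists a medical history. Neither states a family-history question.

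**The case against.** The best defence is that 7.2 already excludes much of the cardiac group and leaves room to exclude the rest. Item 14 allows investigator judgement on the ECG. Item 15 is open-ended, and its named conditions are illustrative. Since 6.1 itself treats family history of long-QT as a QT risk, an investigator who reads the whole protocol could apply item 15 to it. Items 7 and 8 add further discretion. Section 6.1 is also part of the protocol, and the content of the eligibility checklist is not shown.

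Most of this stands, and it limits the point. A reader might infer that 7.2 contains neither exclusion and that such subjects will be enrolled and dosed. The documents do not support that: cardiac disease is partly covered, authority to exclude exists, and screening from 7.2 alone is an inference. What the defence does not remove is the difference between a categorical commitment in 6.1 and discretion in 7.2.

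A reader might also take the exposure to be 24 dosing days with nothing later to catch a problem, or regard these two exclusions as the main remaining safeguard. Neither holds. Exposure to pitolisant is 12 days per subject. Items 14, 15, 20, 22 and 24 also protect against QT risk, and the visit checks and calls continue after entry, although none of them is an ECG.

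**Conclusion.** The inconsistency is real and should be corrected. Of the two history-based exclusions stated in 6.1, family history of long-QT syndrome has no express counterpart in 7.2, and clinically significant cardiac disease has a partial one. A subject excluded by 6.1 could pass the express 7.2 criteria.

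The consequence is a risk of inconsistent screening on a safety rule; the documents do not show that anyone has been or will be wrongly enrolled. How many subjects it could affect is not estimable from them. The estimates, power and alpha are not affected.

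The comparison itself needs no assumption beyond the text. The practical importance assumes that staff lean on 7.2 when they judge eligibility, which is likely but not documented. It also rests on there being no scheduled ECG after baseline, which leaves the entry rules carrying much, though not all, of the QT protection that 6.3 relies on.

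**What to change.** Reconcile 6.1, 7.2 and the eligibility checklist so that all three state the same cardiac and long-QT exclusions. This can be done by carrying the 6.1 commitments into 7.2 and the checklist, or by revising 6.1 to describe the criteria actually applied. Which rule is right is for the sponsor to decide. In either case the IRB should judge risk on the reconciled protections.

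The cost is a short amendment and a checklist update. If the family-history exclusion is kept and no such question is asked now, one must be added at baseline; the documents do not show that the existing medical history is enough. Keeping both exclusions as stated in 6.1 may produce a few more screen failures. No change to the analysis is needed.
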